11.2. Adverse Events

Adverse events will be recorded beginning immediately after the ICF is signed. Subjects will be instructed to report AEs during the study and staff will query subjects regarding AEs throughout the study. The Investigator (and/or designee) must document all AEs reported by the subject from the time subjects give consent through completion of the End-of-Treatment visit. Any subject who is withdrawn from the study due to an AE shall be followed until the event has

resolved or stabilized, and the Investigator will document available follow-up information on the subject's source documentation and CRF.

11.2.1. Definitions of Adverse Events

An AE is any unfavorable and unintended sign (including an abnormal laboratory finding), symptom, or disease temporally associated with the use of medicinal (investigational) product, whether or not related to the medicinal (investigational) product. An AE is any symptom, sign, illness, or experience that develops or worsens in severity during the course of the study. Adverse events reported after consent but before the first dose of study drug are still to be documented by the Investigator but will be considered non-treatment-emergent AEs. Adverse events will be considered treatment emergent if the onset date is after the first dose of study drug.

The severity of each AE will be graded by the Investigator according to the following criteria:

- Mild: awareness of sign or symptom, but easily tolerated
- Moderate: discomfort sufficient to cause interference with normal activities
- Severe: incapacitating, with inability to perform normal activities

Inter-current illnesses or injuries should be regarded as AEs. Abnormal results of laboratory tests or diagnostic procedures are considered to be AEs if the abnormality:

- Is associated with clinical signs or symptoms
- Is considered by the Investigator to be of clinical significance
- Results in study withdrawal
- Fulfills any of the criteria for an SAE, as described in this section
- Requires intervention or further evaluation to determine the etiology of the abnormality and/or assess the risk to the subject
- Requires treatment

An SAE is any untoward medical occurrence at any dose that:

- Results in death
- Is life threatening
- Requires inpatient hospitalization or prolongation of existing hospitalization
- Results in persistent or significant disability/incapacity
- Is a congenital anomaly/birth defect
- Is a medically important event that may jeopardize the subject or may require medical or surgical intervention to prevent one of the other outcomes listed above

The term "life threatening" in the definition of "serious" refers to an event in which the subject was at risk of death at the time of the event; it does not refer to an event that hypothetically might have caused death if it were more severe. Death is an outcome of an event. The event that resulted in death should be recorded and reported on the SAE form and documented in the CRF.

The Investigator must assess the relationship between the AE and the study drug by using the following definitions:

- Probably related: The AE follows a reasonable temporal sequence from administration of the medication; OR the AE follows a known pattern of or response to the study drug; OR an alternative explanation (e.g., concomitant disease, environmental factors, and/or concomitant medication) is less likely than attribution to the study drug; OR the AE diminishes or disappears upon cessation or reduction of dose of medication; OR the AE reappears upon re-administration of the medication.
- Possibly related: The AE follows a reasonable temporal sequence from administration of the medication; OR an alternative explanation (e.g., concomitant disease, environmental factors, and/or concomitant medication) is inconclusive, thus the causal relationship cannot be excluded; OR the AE diminishes or disappears upon cessation or reduction of dose of medication.
- Not related: The AE does not follow a reasonable temporal sequence from administration of the medication; OR the AE does not follow a known pattern of or response to the study drug; OR the AE can be attributed to another factor (e.g., concomitant disease, environmental factors, and/or concomitant medication).

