11.2.4. Reporting of Serious Adverse Events

Reporting of SAEs will be conducted in accordance with the appropriate regulatory guidelines. All SAEs that occur from the time of consent to the End-of-Study visit must be reported, whether or not the event is considered associated with the study drug. The Investigator must complete the SAE Reporting Form and submit it by fax with other relevant source documentation to CSPC Pharma within 24 hours of awareness of the event.

The Investigator must also provide with urgent priority (upon receipt of a request) other relevant documentation (e.g., copies of diagnostic test results, hospital discharge summary, and/or autopsy report) and send this information by fax to CSPC Pharma.

All SAEs must be recorded in the subject's source documentation and documented in the CRF. Medications administered in association with the SAE must be documented in the CRF and in the subject's source documentation. The Investigator must also promptly notify the Institutional Review Board (IRB) /Independent Ethics Committee (IEC) of SAEs, including any follow-up information, in accordance with local institutional policy and applicable regulatory requirements.

Regulatory authorities will be notified of any AE associated with the use of the study drug that is both serious and unexpected, in accordance with the appropriate local regulatory guidelines. Notification of the event will be made by written, expedited safety report.

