5.1.5 Analysis Methods

There will be no formal statistical testing unless indicated otherwise. A summary will be provided for the following TEAEs for each treatment within each study part (Part 1 and 2) (Table 14.3.1.1):

- any AE
- any AE at least possibly related to study medication
- any serious AE
- any AE leading to early withdrawal
- any AE leading to death

The adverse events will be shown by MedDRA system organ class and preferred term, in order of descending overall frequency. For each AE, the percentage of subjects who experience at least 1 occurrence of the given event will be summarized for each treatment within each study part. Incidence tabulations will be provided for overall summary (Table 14.3.1.2), summary by highest severity (Table 14.3.1.3), and summary by relatedness (Table 14.3.1.4).

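### The relatedness definitions join their criteria with OR and give no precedence, so an AE with plausible timing and no known pattern meets all three categories at once

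*Protocol*

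**What the plan says.** Protocol 11.2.1 makes the definitions binding: "The Investigator must assess the relationship between the AE and the study drug by using the following definitions". Three categories follow.

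- *Probably related* has five criteria. It opens with "Probably related: The AE follows a reasonable temporal sequence from administration of the medication", continues "OR the AE follows a known pattern of or response to the study drug", then covers a less likely alternative explanation and improvement on cessation or dose reduction, and ends "OR the AE reappears upon re-administration of the medication".
- *Possibly related* opens with the same timing criterion and repeats the improvement criterion. Its third criterion is an inconclusive alternative explanation.
- *Not related* is met by implausible timing, or by "OR the AE does not follow a known pattern of or response to the study drug", or by attribution to another factor.

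Protocol 11.2.3 asks for the investigator's opinion on whether the drug could reasonably have caused the AE, but refers back to 11.2.1 for how to form it. SAP 5.1.4 carries the three categories over unchanged. SAP 5.1.5 then summarises "any AE at least possibly related to study medication" in Table 14.3.1.1 and tabulates TEAEs by relatedness in Table 14.3.1.4. Protocol 12.7 also summarises AEs by relationship. On expedited reporting, Protocol 11.2.4 says: "Regulatory authorities will be notified of any AE associated with the use of the study drug that is both serious and unexpected".

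**The concern.** A classification meant to put each AE in one category should not place it in categories that contradict each other. Here *probably* and *possibly* share two criteria, and *not related* has a sufficient criterion that plausible timing does nothing to exclude. Two investigators who follow the text faithfully can record opposite answers for the same event.

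The treatment of new kinds of reaction is the most awkward part. Not resembling what is already known about a drug is weak evidence against causation, yet the text lets it settle the matter. Section 11.2.4 expects that some events will be both associated with the drug and unexpected, while 11.2.1 allows an event outside the known pattern to be called unrelated for that reason alone. Section 11.2.5 makes an SAE that comes to attention within 30 days after cessation reportable if the investigator sees a reasonable possibility of causation. After the End-of-Study visit, reporting therefore depends on the same causality judgement.

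**Working it through.** The plan gives no figure to reproduce. The check is whether the three definitions can hold together.

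Inputs, all from Protocol 11.2.1: T = plausible timing; K = known pattern; D = improvement on cessation or reduction; R = recurrence on re-administration. The alternative explanation is in one of three states: L = less likely than the drug, I = inconclusive, F = the AE is attributable to another factor.

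Rules as written:

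- Probably = T or K or L or D or R
- Possibly = T or I or D
- Not related = (not T) or (not K) or F

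Take first the simplest reading for a single-dose period, with D and R false. That leaves 2 × 2 × 3 = 12 profiles:

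| T | K | Alternative | Categories met |
|---|---|---|---|
| yes | yes | L | probably, possibly |
| yes | yes | I | probably, possibly |
| yes | yes | F | all three |
| yes | no | L | all three |
| yes | no | I | all three |
| yes | no | F | all three |
| no | yes | L | probably, not related |
| no | yes | I | all three |
| no | yes | F | probably, not related |
| no | no | L | probably, not related |
| no | no | I | possibly, not related |
| no | no | F | not related |

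All three categories: 1 + 3 + 1 = 5 of 12. At least two: 11 of 12. Exactly one: 1 of 12. Every profile with plausible timing and no known pattern meets all three (3 of 3), and every profile without a known pattern meets *not related* (6 of 6).

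Letting D and R vary gives 12 × 4 = 48 profiles. Of these, 31 meet all three categories, 47 meet at least two and 1 meets exactly one. Plausible timing without a known pattern again meets all three every time (12 of 12). If L, I and F may also occur together there are 16 × 8 = 128 profiles: 94 meet all three and 126 at least two. The result does not depend on how the alternative explanation is coded.

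Setting D to false is the lenient choice. Each period is one dose, so an AE that resolves can be read as having resolved after cessation, and that satisfies both *probably* and *possibly*.

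**The case against.** The best defence is that these are prompts for clinical judgement rather than Boolean rules. Section 11.2.3 asks for an opinion, and the alternative-explanation clauses do form a sensible scale: less likely than the drug, inconclusive, attributable elsewhere. An experienced investigator would probably use that scale. This makes it too strong to call every choice arbitrary, but it does not cure the text. Section 11.2.1 says the definitions must be used, 11.2.3 points back to them, and no precedence is given.

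The defence is right about reach, and several stronger readings that a reader might infer are not supported.

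- *SAEs could be kept from the sponsor.* Section 11.2.4 requires every SAE from consent to End-of-Study to be reported, whatever its association with the drug. Its IRB/IEC sentence has no relatedness condition either. Only regulatory notification requires association, and that word is not expressly tied to the 11.2.1 grades.
- *Every unexpected AE is by definition not related.* The protocol does not define unexpected. Equating it with lack of a known pattern is close, but it is an interpretation.
- *The related-AE count is anyone's guess.* For events that meet all three categories, the rule permits a count of none or all of them. That is a logical bound on a subset of unknown size. Section 11.2.2 lists many common complaints as associated reactions, including headache, dizziness, fatigue and nausea, so the subset may be small.
- *One product is favoured.* The trial is open-label, so the investigator knows the product when choosing a category. Both products are judged by the same definitions, and nothing in the documents shows a direction of bias.

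The affected outputs are also descriptive. The SAP plans no hypothesis test on safety, all AEs are recorded regardless of relationship, and the overall, preferred-term and severity summaries do not use relatedness.

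**Conclusion.** The relatedness rule is wrong as written: followed literally, it returns contradictory answers. An AE with plausible timing and no known pattern is *probably*, *possibly* and *not related* together, and lack of a known pattern alone is enough for *not related*.

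The direct effect in the SAP is on one row of Table 14.3.1.1 and on Table 14.3.1.4. There is also a conflict to reconcile with the notification of associated, serious and unexpected AEs in 11.2.4 and with the 30-day SAE rule in 11.2.5. The bioavailability and food-effect conclusions, sample size and power are untouched.

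This rests on reading OR as making each criterion sufficient, which is its plain meaning, and on the absence of a tie-break in either document. The profile counts describe the logic of the rule; they do not predict how many AEs will be affected.

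**What to change.** In Protocol 11.2.1, remove absence of a known pattern as a sufficient criterion for *not related*, and apply the categories in order:

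1. *Not related*: implausible timing, OR clearly attributed to another cause.
2. *Probably related*: not (1), AND plausible timing, AND an alternative explanation less likely than the drug, AND at least one of known pattern, improvement after stopping, or recurrence on re-administration.
3. *Possibly related*: every other AE with plausible timing.

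Add: if in doubt, record the more related category.

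The order makes the categories exclusive and exhaustive. On the same 12 profiles, 8 become *not related* (the 6 with implausible timing and the 2 with plausible timing but another cause), 1 *probably* (plausible timing, known pattern, alternative less likely) and 3 *possibly*, so 8 + 1 + 3 = 12 with no overlap and no gap. A new kind of event with plausible timing and no other established cause is at least *possibly related*, which removes the conflict with 11.2.4 and 11.2.5. The wording should also say how improvement after stopping is to be judged when each period is a single dose.

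The cost is protocol wording and any matching CRF guidance. The three category names stay, so the SAP tables need no restructuring. The small downside is that some AEs move to a more related category.

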11.2.2. Adverse Events of Special Interest

The following adverse events of special interest that are considered to be associated with the levamlodipine maleate tablets will be collected:

Common adverse reactions:

- Autonomic nerves system: flushing
- Body as a Whole: Fatigue
- Cardiovascular, general: edema
- Central and peripheral nervous system: Headache, Dizziness
- The gastrointestinal tract: abdominal pain, nausea Heart rate/rhythm: palpitations Psychological: sleepiness
- In clinical trials found no clinical laboratory abnormalities associated with this product.

Rare adverse reactions in post-marketing experience:

- Autonomic nerves system: dry mouth, perspiration
- Body as a Whole: weakness, back pain, body discomfort, pain, weight increase/decrease
- Cardiovascular, general: hypotension, syncope
- Central and peripheral nervous system: high muscle tension, hypesthesia/paresthesia, peripheral neuropathy, tremor
- Endocrine: hyperplasia of mammary glands
- The gastrointestinal tract: constipation: dyspepsia (including gastritis), gingival hyperplasia, pancreatitis, vomiting

- Metabolic/nutritional: hyperglycemia Musculoskeletal: arthralgia, muscle cramps pain, muscle pain
- Platelet/bleeding and clotting: purpura, thrombocytopenic purpura
- Psychological: impotence, insomnia, mood changes
- Respiratory system: cough, dyspnea
- Dermatologic: baldness, epichrosis
- Special feeling: taste disorder, tinnitus
- Urinary system: frequent micturition
- blood vessels (extracardiac) : vasculitis
- Vision: visual disturbance
- White blood cells/reticuloendothelial system: leucopenia

There have been rare reports of anaphylaxis caused by amlodipine, including pruritus, rash, vasogenic edema and erythema multiforme.

11.2.3. Recording Adverse Events

All AEs (regardless of seriousness or relationship to study drug) including those from the time of consent to the End-of-Treatment visit are to be recorded in the subject's source documents and on the corresponding page(s) in the CRF. Whenever possible, symptoms, signs, and laboratory abnormalities should be grouped as a single syndrome or diagnosis. The Investigator should specify the date of onset, intensity, action taken with respect to study drug, corrective treatment/therapy given, outcome and his/her opinion as to whether there is a reasonable possibility that the AE was caused by the study drug, according to the definitions noted in Section 11.2.1. All medications administered to treat an AE must be recorded in the subject's source documentation and documented in the CRF.

11.2.4. Reporting of Serious Adverse Events

Reporting of SAEs will be conducted in accordance with the appropriate regulatory guidelines. All SAEs that occur from the time of consent to the End-of-Study visit must be reported, whether or not the event is considered associated with the study drug. The Investigator must complete the SAE Reporting Form and submit it by fax with other relevant source documentation to CSPC Pharma within 24 hours of awareness of the event.

The Investigator must also provide with urgent priority (upon receipt of a request) other relevant documentation (e.g., copies of diagnostic test results, hospital discharge summary, and/or autopsy report) and send this information by fax to CSPC Pharma.

All SAEs must be recorded in the subject's source documentation and documented in the CRF. Medications administered in association with the SAE must be documented in the CRF and in the subject's source documentation. The Investigator must also promptly notify the Institutional Review Board (IRB) /Independent Ethics Committee (IEC) of SAEs, including any follow-up information, in accordance with local institutional policy and applicable regulatory requirements.

Regulatory authorities will be notified of any AE associated with the use of the study drug that is both serious and unexpected, in accordance with the appropriate local regulatory guidelines. Notification of the event will be made by written, expedited safety report.

11.2.5. Adverse Event Follow-up

The Investigator should take all appropriate measures to ensure the safety of the subjects, including referral to a specialist if indicated. The Investigator should follow up on the outcome of any AE until the event has resolved or stabilized.

This implies that follow-up may continue after the subject discontinues from the study and that additional information may be requested.

Any SAE brought to the attention of the Investigator within 30 days after cessation of study drug and considered by him/her to be caused by the study drug with a reasonable possibility, should be reported through the SAE reporting process.

12. STATISTICAL METHODOLOGY

12.1. Sample Size Determination

Based on an approximate CV_B of 20%, a CV_W is calculated to be 14% for C_{max} and 11% for $AUC_{0-\infty}$, respectively. Thus, an N value of approximately 18 completed subjects for AUC (%CV rounded off to 10%), an N value (interpolated) of approximately 27 completed subjects would be required for the proposed bioequivalence study. With an estimated drop-out rate of 20% in this cross-over study, approximately 32 subjects will be enrolled.

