1. PROTOCOL SYNOPSIS

Name of Sponsor/Company

CSPC Ouyi Pharmaceutical Co., Ltd, a subsidiary company within CSPC Pharmaceutical Group, Ltd (CSPC)

Title of Study

A Randomized, Open-label, Single-Dose, Two-Way Crossover Study to Assess the Relative Bioavailability of 5 mg of Levamlodipine Maleate Tablets versus 10 mg of Amlodipine Besylate Tablet (NORVASC[®] from Pfizer Inc.) in Healthy Subjects Followed by a Phase to Study Food Effect on the PK Profile of Levamlodipine

Phase of Development

Phase 1

Investigational Product, Dosage and Mode of Administration

Levamlodipine Maleate Tablet is a new investigational drug for the treatment of hypertension and Coronary Artery Disease (CAD) chronic stable angina. Levamlodipine is the pharmacologically active isomer in amlodipine, which presents in amlodipine as a 1:1 mixture with the (R)amlodipine. The to-be-marketed dosage strengths planned in the US are 1.25, 2.5 and 5 mg of levamlodipine maleate tablets with an anticipated dosage regimen of once daily.

Name of Active Ingredient

Levamlodipine, the (S)amlodipine

Reference Therapy, Dosage and Mode of Administration

Amlodipine Besylate Tablet (NORVASC[®] from Pfizer Inc.)

Study Center

Collaborative Neuroscience Network, LLC (CNS)

[name]

[name]

Principal Investigator

[name]

Objectives

The objectives of this study are (1) to assess the relative bioavailability (BA) of a single oral dose of either 5 mg of Levamlodipine Maleate Tablets from CSPC or 10 mg of Amlodipine Besylate Tablet (NORVASC[®]) from Pfizer Inc. under fasting condition in male and female healthy subjects; and (2) to evaluate food effect on the PK profile of Levamlodipine Maleate Tablets from CSPC.

Study Design

This study consists of 2 parts:

Part 1 will be a randomized, open-label, single-dose, two-way crossover study to assess the relative BA of levamlodipine maleate tablets from CSPC (Test) versus Amlodipine Besylate Tablet NORVASC[®] from Pfizer Inc. (Reference) after a single oral administration under fasted conditions in male and female healthy subjects. Approximately 32 healthy subjects will be enrolled in the US to obtain 27 completed subjects.

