5. INVESTIGATIONAL PLAN

5.1. Study Design

This study consists of 2 parts. **Part 1** will be a randomized, open-label, single-dose, two-way crossover study to assess the relative BA of 5 mg of levamlodipine maleate tablets from CSPC (Test Product) versus 10 mg of Amlodipine Besylate Tablet NORVASC[®] from Pfizer Inc. (Reference Product) after a single oral administration under fasted conditions in male and female healthy subjects. Approximately 32 healthy volunteers will be enrolled for Part 1 to obtain 27 completed subjects.

Part 2 will be a single-arm, open-label, single-dose phase to assess food effect on the PK profile of levamlodipine maleate tablets from CSPC. Subjects who have completed Part 1 will be rolled over to Part 2 after a wash-out period for at least 14-days since the last dosing. Subjects will

receive a single oral administration of 5 mg levamlodipine maleate tablets from CSPC under a high-fat/high-calorie meal that should derive approximately 150, 250 and 500-600 calories from protein, carbohydrate and fat, respectively.

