5.3. Number of Subjects

The planned total subject number is about 32 healthy volunteers for Part 1 in order to obtain 27 completed subjects. Subjects who have completed Part 1 will be rolled over to Part 2 to assess food effect on the PK profile of levamlodipine maleate tablets.

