1.4 Randomization

In Part 1, subjects will be assigned in a ratio of 1:1 to receive one of two treatment sequences (RT or TR; R=10 mg of NORVASC® and T=5 mg of levamlodipine maleate tablets). Each sequence will have 16 subjects randomized for a total of 32 patients. {The text presented in this section had been edited from that in Section 8.1 of the protocol. See Section 8 of this SAP for further details}

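### Enrolling 32 at the stated 20% drop-out gives about 25–26 completers, not the required 27; 32 yields 27 only if drop-out is about 15.6%

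*Protocol*

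**What the plan says.** Protocol 12.1 derives the size from within-subject CVs of 14% for Cmax and 11% for AUC. It concludes that "an N value (interpolated) of approximately 27 completed subjects would be required for the proposed bioequivalence study", and it closes with the enrolment figure: "With an estimated drop-out rate of 20% in this cross-over study, approximately 32 subjects will be enrolled". SAP 1.3 carries the same text.

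The pairing of 32 enrolled with 27 completing also appears in the synopsis ("Approximately 32 healthy subjects will be enrolled in the US to obtain 27 completed subjects", and again under the planned subject number), in Protocol 5.1 ("Approximately 32 healthy volunteers will be enrolled for Part 1 to obtain 27 completed subjects"), in Protocol 5.3 ("The planned total subject number is about 32 healthy volunteers for Part 1 in order to obtain 27 completed subjects") and in SAP 1.2. SAP 1.4 fixes the randomised number: "Each sequence will have 16 subjects randomized for a total of 32 patients". Protocol 8.1 also gives 16 per group.

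Neither document gives another drop-out rate or a rule for replacing subjects who leave.

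**The concern.** The plan calls 27 completers the number required, yet its own drop-out estimate applied to its own enrolment gives fewer. The number needed is found by dividing the completer target by the expected completion fraction, and that calculation does not give 32.

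At stake is whether the sample-size statement is true as written. A reader will take it that 32 enrolled covers a 20% loss and still leaves 27. On the plan's assumptions, missing 27 is more likely than reaching it. Part 2 takes only subjects who complete Part 1, so it inherits whatever number results, although the plan sets no separate target for Part 2.

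The plan also gives no target power and no assumed test/reference ratio. A reader therefore has no way to see what 25 or 26 completers would cost, because 27 is the only benchmark offered.

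**Working it through.** **Inputs from the documents**
- Completers required: n = 27 (Protocol 12.1, SAP 1.3)
- Drop-out: d = 0.20 (same sections)
- Enrolled: N = 32 (same sections; 16 per sequence in SAP 1.4)
- Within-subject CV for Cmax: 14% (Protocol 12.1)
- Acceptance limits 80–125% with a 90% confidence interval (synopsis, Statistical Methods), which is equivalent to two one-sided tests at 5% each

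**Reproducing the stated 32**
- n × (1 + d) = 27 × 1.20 = 32.4, which rounds to 32.
- n / (1 − d) = 27 / 0.80 = 33.75, which rounds up to 34.

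The stated figure is consistent with multiplying by 1.2. The documents show no formula, so this origin is an inference, and the mismatch does not depend on it.

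**Working back from 32**
- Expected completers at 20% drop-out: 32 × 0.80 = 25.6, which is 1.4 below 27.
- Drop-out at which 32 gives 27: 1 − 27/32 = 5/32 = 15.6% (84.4% completing).

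**Chance of reaching 27**

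The number completing is taken as binomial, with subjects independent.

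| Enrolled | Drop-out | Expected completers | P(at least 27) |
|---|---|---|---|
| 32 | 20% | 25.6 | 0.36 |
| 34 | 20% | 27.2 | 0.63 |
| 32 | 15% | 27.2 | 0.65 |

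The probability of at least 25 completers with 32 enrolled at 20% drop-out is 0.70.

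**Cost in power for Cmax**

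The log-scale within-subject SD is √ln(1 + 0.14²) = 0.139. The standard error of the log ratio is 0.139 × √[½(1/n₁ + 1/n₂)], with completers split as evenly as possible between the sequences and n − 2 degrees of freedom. Power is the probability that the 90% interval lies inside 80–125%, integrated over the distribution of the residual SD. The true ratios are assumptions, since the plan states none.

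| Assumed true ratio | 27 completers | 26 completers | 25 completers | Loss, 27 to 25 |
|---|---|---|---|---|
| 0.95 | 99.7% | 99.6% | 99.5% | 0.2 points |
| 0.90 | 91.5% | 90.6% | 89.5% | 2.0 points |
| 0.88 | 78.8% | 77.4% | 75.8% | 3.0 points |

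**The case against.** The strongest reply is that the gap is trivial: 1.4 expected completers, or two enrolled subjects. Every figure is hedged, since 27 is approximate and interpolated, 20% is an estimate and 32 is approximate. The power loss is at most about 3 points over the ratios examined, and the 0.88 case that gives the largest loss has no basis in the documents. The 36% also treats a planning estimate as exact, and even the correctly inflated 34 reaches 27 only 63% of the time. Finally, 32 may have been chosen as a convenient even number for 16 per sequence rather than by a wrong formula.

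Most of this stands as a limit on the size of the point. The study is not shown to be underpowered, the origin of 32 is unproven, and no shortfall can be demonstrated for Part 2. It does not remove the inconsistency, however. The hedging does not make 27, 20% and 32 agree, because SAP 1.4 randomises exactly 32 and no replacement rule makes up the difference. At 34 enrolled the expected number at least meets the target; at 32 it does not.

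**Conclusion.** The concern holds. At 20% drop-out, 32 enrolled gives an expected 25.6 completers against a stated requirement of 27. Meeting 27 on average takes 34 enrolled, or a drop-out of about 15.6% with 32. This part rests only on the plan's own figures.

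The 36% chance of reaching 27 also assumes independent completion at exactly 80%. The power effect, roughly 0.2 to 3 percentage points for Cmax, depends on assumed ratios of 0.95 to 0.88. The 27 itself cannot be checked, because target power and ratio are not stated.

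This is an arithmetic inconsistency in the sample-size justification, repeated in both documents. It should be corrected, but it is not a failure of power.

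**What to change.** Keep 32 enrolled and make the statement true in one of two ways.

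1. **Keep 20% and restate the yield.** Say that 32 enrolled is expected to give 25–26 completers, and give the power at that number with the assumed test/reference ratio. This changes the synopsis (both places), Protocol 5.1, 5.3 and 12.1, and SAP 1.2 and 1.3.
2. **Keep 27 and restate the drop-out.** Give the rate that 32 covers, about 15% (27/0.85 = 31.8, so 32), with a reason for expecting it, since the documents offer no evidence for that rate. Only Protocol 12.1 and SAP 1.3 state a drop-out rate, so only they need the new figure; the other sections should be checked for agreement.

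The first option keeps the sponsor's own drop-out estimate and supplies the missing power and ratio. Under the second, those two inputs should still be added to Protocol 12.1 and SAP 1.3.

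The cost is wording and a slightly less favourable stated figure, with no extra subjects or procedures. SAP section 7 already records a correction to Protocol 8.1 and can record this one. If the sponsor prefers to hold both 27 and 20%, the consistent enrolment is 34 (17 per sequence). That adds two subjects and also changes Protocol 8.1 and SAP 1.4. The small power loss does not make it necessary.
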